## Introduction

Direct conventional laryngoscopy is an essential skill in airway management for endotracheal intubation. Although the majority of direct laryngoscopies are uneventful in experienced hands, it can be difficult and challenging in some situations such as limited mouth opening, limited mandibular protrusion, narrow dental arch, decreased thyromental distance, modified Mallampati class 3 or 4, decreased submandibular compliance, decreased sterno-mental distance, limited head and upper neck extension, and increased neck circumference (1,2). Due to these challenging situations, complications may occur due to unintended teeth, lips, gingiva, and oral tissue damage during laryngoscopy, particularly in patients with difficult intubation (3).

Dental injury is not only one of the most common complications in the oral cavity during laryngoscopy but also an important part of medicolegal claims against anesthetists (4,5). Enamel infractions or fractures, loosened or subluxated teeth, tooth avulsion, and crown or root fractures are commonly reported dental injuries with an incidence as high as 38.6% (6). Unfortunately, complications may still occur even in patients without known predictors of difficult intubation and some of these injuries are microscopic and cannot be noticed by the clinicians and diagnosed after the patients' complaints (5). Thus, dental damage may occur more often than estimated.

Visual inspection and radiography are the conventional diagnostic methods in the dental practice. However, with these methods, it is not always possible to diagnose dental problems in depth and definitively. Transillumination as a diagnostic tool in medicine refers to light transmission through parts of the body. Fiber-optic transillumination (FOTI) and near-infrared light transillumination (NILT) are the additional detection methods used for the diagnosis and assessment of dental caries (7). FOTI of teeth is an easy, well-tolerated, non-invasive, and non-irradiating technique and has been used for over 100 years (8).

This study aims to investigate especially minor dental traumas and associated damages instead of major traumas that can be directly seen due to conventional laryngoscopy using transillumination technique with cold light source.

## **Material and Methods**

After the approval of the Selcuk University Local Institutional Ethics Committee (2017/05), 300 ASA I-III adult patients who underwent elective surgical operations under general anesthesia and underwent endotracheal intubation were included in this prospective, double-blinded study. Written informed consent was obtained from each patient during the preoperative anesthetic evaluation.

During the preoperative anesthetic evaluation, an anesthetist and dentist in the study team performed a detailed oral physical examination on all study patients. Demographic data such as age, gender, body weight, height, data related to airway management such as mallampati score, thromental distance, mouth opening size, and information about past anesthesia history, including previously described difficult intubation and medical condition, were questioned, and recorded. During a dental examination, all teeth, but particularly anterior 6 of maxillary and mandibular teeth, were examined regarding general dental hygiene and the existence of any missing teeth, tooth decay, plaque and stone formation, discoloration, gum problems such as recession and gingivitis, and tooth trauma. The patients with the presence of deformation due to a trauma or a congenital abnormality in the maxilla-fascial region, a swinging tooth, and a history of previous surgical operation regarding the maxilla-fascial region and oral cavity were not included in the study.

All patients were subjected to the same anesthetic process. None of the patients were given anesthetic premedication on the day of surgery. Anesthesia induction was achieved with  $2.0 \text{ mg} \cdot \text{kg}^{-1}$  iv propofol,  $2.0 \text{ mg} \cdot \text{kg}^{-1}$  iv fentanyl, and  $0.6 \text{ mg} \cdot \text{kg}^{-1}$  iv rocuronium after routine monitoring with ECG, non-invasive blood pressure, and  $\text{SpO}_2$ . Each patient was ventilated with a face mask with 100%  $\text{O}_2$  for 2-3 minutes and intubated with a proper endotracheal tube by the same anesthetist using a conventional laryngoscope. All intubations were achieved by anesthesiologists with different statuses (senior assistants and consultants who were blind to the study). After the endotracheal intubation, the anesthesiologist included in the study recorded the data about intubation and airway management such as

Cormack-Lehane Score, laryngoscope blade type and size, difficulty in intubation, use of additional devices such as oral airway, intubating supraglottic airway device, video laryngoscope, and intubating guide in the airway management, and the number of intubating attempts by asking the practitioner.

The intraoperative dental evaluation was performed using a transillumination technique with a cold light source at two different time points: T1: Before anesthesia induction, and T2: After endotracheal intubation, before the start of the surgical operation. The same dentist performed all dental evaluations. Although all teeth were evaluated, the evaluation with the cold light source was particularly for every six teeth in the lower and upper jaws.

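### The study is labelled double-blinded, but it is a single-group before/after study in which the dentist reading T1 and T2 cannot be masked to time point

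*Combined protocol and SAP*

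**What the plan says.** All references are to the combined protocol and SAP.

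- **Label.** Material and Methods says the patients "were included in this prospective, double-blinded study".
- **Groups.** The same section describes one anesthetic process for everyone. No randomisation, allocation or control arm appears. Statistical Analysis names tests for group comparisons but defines no groups.
- **Who is blind.** The only other statement on blinding concerns the intubating staff: "senior assistants and consultants who were blind to the study".
- **Who reads the outcome, and when.** "The same dentist performed all dental evaluations", at two times: "T1: Before anesthesia induction, and T2: After endotracheal intubation, before the start of the surgical operation". The reading is done on the patient with a cold light source. No stored images, second reader or repeat reading are described.
- **Who records intubation data.** An anesthesiologist of the study team, not the dentist, records the airway and intubation details, including "the number of intubating attempts by asking the practitioner".
- **Preoperative visit.** "an anesthetist and dentist in the study team performed a detailed oral physical examination on all study patients". Airway measurements and any earlier difficult intubation were collected at this visit; the text does not say who wrote them down.
- **Analysis.** Statistical Analysis compares readings before and after intubation with paired t or Wilcoxon signed-rank tests, and relates intubation variables to dental trauma by logistic regression.

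**The concern.** Double-blinded normally tells a reader that two parties, usually including whoever judges the outcome, did not know something that could sway them. Here there is no allocation to conceal, one party is said to be blind to something unspecified, and the person judging the outcome is not said to be blind to anything.

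The Introduction aims at minor damage that ordinary inspection would miss, where a finding depends most on the reader's judgement. The dentist at T2 made the T1 reading and knows that laryngoscopy has since taken place. If that knowledge lowers the threshold for calling a mark new, the paired comparison counts the shift as injury. Nothing else in the design would reveal it. A reader who trusts the label would assume a protection that is not described.

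**Working it through.** **1. Masking, role by role**

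| Role | What the text says | Masked? |
|---|---|---|
| Intubating staff | Blind to the study | Yes, but to what is not stated |
| Dentist (T1 and T2) | Same person, both times | Not stated; time point cannot be masked |
| Recording anesthesiologist | Asks the operator after intubation | Not stated |
| Patient | Nothing | Not stated |

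One role is described as blind, and there is one group. That the dentist knows the time point is an inference, but a firm one: the patient has had no premedication and is awake at T1, and is anesthetised and intubated at T2. No later reading in concealed order is described.

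**2. How many misreadings would matter to the paired test**

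The documents give no reading-error rate, expected incidence or scoring rule, so this is an illustration. Inputs: n = 300 (Material and Methods). Assumed: a 0/1 score per patient, k patients read as newly injured and j read the opposite way.

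Asymptotic test: z = (k − j)/√(k + j). Exact test: two-sided binomial on the k + j discordant patients.

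- k = 4, j = 0: z = 4/√4 = 2.00, p = 0.0455 (paired t: p = 0.045). With k = 3, p = 0.083.
- Exact, k = 6, j = 0: p = 2 × (1/2)^6 = 0.031. With k = 5, p = 0.063.

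| Opposite readings j | Smallest k, t or asymptotic | Smallest k, exact | Exact k as % of 300 |
|---|---|---|---|
| 0 | 4 | 6 | 2.0 |
| 1 | 7 | 8 | 2.7 |
| 2 | 9 | 10 | 3.3 |
| 3 | 11 | 12 | 4.0 |

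The lowest threshold is 4/300 = 1.3%. Once true injuries reach the threshold, the test is significant without any misreading. So misreading can decide the test only if true injury is below about 1.3% to 4.0%.

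At higher rates (j = 0):

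- Assumed 10%: 30 patients, z = √30 = 5.48. Adding 6 misreadings gives z = √36 = 6.00.
- The 38.6% cited in the Introduction as an upper figure: 0.386 × 300 ≈ 116 patients, z = √116 = 10.77. Adding 6 gives z = √122 = 11.05.

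Significance does not change in either case.

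**3. Effect on the reported incidence**

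At any true rate, 4 to 6 misreadings add 4/300 to 6/300, or 1.3 to 2.0 percentage points. Relative to the true count this is 67% to 100% at 2% (6 patients), 13% to 20% at 10%, and 3.4% to 5.2% at 38.6%.

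**4. Odds ratios, only if the dentist knew airway or intubation data**

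Assume a true OR of 1, true risk p, and an extra fraction f of uninjured patients over-read in the difficult-airway group only. Then q = p + (1 − p)f and OR = [q/(1 − q)]/[p/(1 − p)].

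| p | f = 1% | f = 2% | f = 5% |
|---|---|---|---|
| 2% | 1.51 | 2.02 | 3.63 |
| 10% | 1.10 | 1.20 | 1.53 |
| 38.6% | 1.03 | 1.05 | 1.14 |

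Sampling error is large where these are highest. Take p = 2%, f = 1% and half of the 300 exposed. Expected events are 150 × 0.0298 = 4.47 and 150 × 0.02 = 3. The standard error of log OR is √(1/4.47 + 1/145.53 + 1/3 + 1/147) = 0.755, so OR 1.51 has an expected 95% CI of about 0.34 to 6.6. On the same basis OR 2.02 has about 0.49 to 8.3.

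**The case against.** Several points on the other side are sound.

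- **The recording roles are separate.** Intubation data go to a study anesthesiologist, so the dentist may well have been unaware of the intubation course. That could be what the second half of the label means. It is a possible reading, but the documents do not state it, and it would not mask the time point.
- **Live before/after examination is inherently unmasked in time.** The plan has a within-patient baseline read by the same dentist, and T2 comes before surgery starts. The baseline deals with damage already present, but not with a threshold that changes between readings. Using one reader is not a fault.
- **The arithmetic bites only in a corner.** Near the one incidence the documents cite, neither significance nor incidence moves much, and the Introduction argues that injury may be commoner than thought. This stands and limits the size of the concern.

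A reader might go further and infer that the dentist knew which airways were difficult and that the odds ratios are therefore biased. The text does not support that: it places a study-team dentist at the preoperative visit but does not say who recorded the airway data or what was known at T2. A reader might also infer that the T1/T2 result is an artefact, or that the study's primary endpoint is compromised. No misreading is shown, and no primary endpoint is named.

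Material and Methods also says patients were "intubated with a proper endotracheal tube by the same anesthetist using a conventional laryngoscope" and then "All intubations were achieved by anesthesiologists with different statuses". These need to be reconciled, but that is a separate matter of who intubated and has no bearing on the dentist's masking.

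**Conclusion.** The concern holds as a mismatch between the stated and the described design. The label claims double blinding; the text supports one group, one role said to be blind to something undefined, and an outcome assessor who cannot be masked to time point. This holds at any injury rate and does not depend on the illustration.

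The consequence for the results is narrower. A threshold shift cannot be separated from true minor injury in the paired comparison, and its size and direction are unknown. On a 0/1 score with one-directional error, it could decide significance only if true injury is very low, roughly under 1% to 4%. The incidence estimate would rise by 1.3 to 2.0 points for every 4 to 6 misreadings, which is important at low rates and minor near 38.6%. Any effect on the odds ratios is conditional on what the dentist knew, and at low incidence would mostly be lost in sampling error. Every rate used except the cited 38.6% is an assumption.

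It should be fixed because readers will rely on the label and correcting it costs almost nothing.

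**What to change.** 1. **Correct the label.** Replace the double-blinded description with: *single-group before/after study; outcome assessor not masked to time point; intubating staff unaware of [state what]*. Report the T1/T2 difference as an unmasked before/after reading. This is wording only; the downside is a less favourable design label.
2. **Settle what the dentist knew.** For any patients still to be assessed, keep the dentist away from the laryngoscopy and withhold airway and intubation data until T2 is recorded. This is a small change in working order; it protects the regression but does not mask the time point. If collection is complete, as the past-tense methods suggest, state what the dentist knew and report it as a limitation of the odds ratios.
3. **Only if T1 and T2 images already exist** (the documents mention none): have the same dentist re-score them in random order, without patient or time-point labels, as a sensitivity analysis beside the live reading. This costs reading time, and the reader may recall some cases.

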#### Statistical Analysis

The statistical analysis was performed using SPSS, version XX. The normality of continuous variables was assessed with the Kolmogorov-Smirnov test. Descriptive statistics were presented as mean  $\pm$  standard deviation (SD) or median (interquartile range, IQR) for continuous variables and as frequency (n) and percentage (%) for categorical variables. Group comparisons were made using the Independent Samples t-test, Mann-Whitney U test, One-Way ANOVA, or Kruskal-Wallis test, depending on the data distribution. Categorical variables were compared using the Chi-square test or Fisher's exact test. The relationship between intubation variables and dental trauma was analyzed using logistic regression, and results were reported as odds ratios (OR) with 95% confidence intervals (CI). Paired sample t-tests or Wilcoxon signed-rank tests were employed to compare dental evaluations before and after intubation. A p-value  $< 0.05$  was deemed statistically significant.

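### Does the logistic model need a stated unit, covariate list and operator-grade adjustment before its odds ratios can be trusted?

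*Combined protocol and SAP*

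**What the plan says.** The Statistical Analysis section states that "The relationship between intubation variables and dental trauma was analyzed using logistic regression", with results given as odds ratios and 95% confidence intervals. For the before-and-after comparison it says "Paired sample t-tests or Wilcoxon signed-rank tests were employed to compare dental evaluations before and after intubation". Neither sentence names the unit of analysis. The section gives no covariate list and no model for several teeth in one mouth.

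Material and Methods describes two cold-light examinations, one before induction and one after intubation, and adds: "Although all teeth were evaluated, the evaluation with the cold light source was particularly for every six teeth in the lower and upper jaws". That makes up to 12 index teeth per patient.

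After intubation a study anesthesiologist "recorded the data about intubation and airway management such as" the Cormack-Lehane score, blade type and size, difficulty, four kinds of additional device, and "the number of intubating attempts by asking the practitioner". These are nine named items in an open list. Operator grade is not named in it.

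On who intubated, one sentence says that each patient was "intubated with a proper endotracheal tube by the same anesthetist using a conventional laryngoscope". The next reads: "All intubations were achieved by anesthesiologists with different statuses (senior assistants and consultants who were blind to the study").

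**The concern.** Three omissions seem to combine.

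- **Unit.** With 12 index teeth per patient, a data set of 300 rows and one of up to 300 × 12 = 3,600 rows are both conceivable. Every named test assumes independent rows, or independent pairs. If teeth were rows, confidence intervals for patient-level predictors such as number of attempts would be too narrow.
- **Covariates and target effect.** A reader cannot tell whether the odds ratios are crude or adjusted, or whether they describe total or direct effects.
- **Operator.** The two sentences can be read as contradictory. With a single operator, grade cannot confound. With senior assistants and consultants both intubating, a crude odds ratio for something chosen after the operator was assigned, such as blade type, could partly reflect grade.

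At stake are the risk-factor odds ratios. The aim in the Introduction, detecting minor dental damage from laryngoscopy, rests on the before-and-after examination, which has no exposure contrast for grade to distort.

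**Working it through.** The plan has no figure of its own on this point to reproduce. Two inputs come from the documents: 300 patients, and the cited background figure, "commonly reported dental injuries with an incidence as high as 38.6" per cent. The 12 index teeth follow from six per jaw. Everything else below is assumed and shown as a range.

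**1. Teeth as independent rows.** Design effect = 1 + (12 − 1) × ICC. Actual size of a nominal 5% test = 2 × [1 − Φ(1.96/√design effect)].

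| ICC (assumed) | Design effect | Actual size |
|---|---|---|
| 0.05 | 1.55 | 0.115 |
| 0.10 | 2.10 | 0.176 |
| 0.20 | 3.20 | 0.273 |
| 0.30 | 4.30 | 0.345 |

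A beta-binomial simulation used 300 patients, 12 teeth, 20% exposed and 3,000 runs. Tooth rows rejected in 11% to 35% of runs when 20% or 38.6% of patients had trauma, and in 6% to 25% when 5% did. One outcome per patient rejected in 3% to 5% throughout. Missing teeth are noted at the preoperative examination, so 12 is a maximum.

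**2. Which unit the text supports.** The study population is counted as 300 patients. The intubation variables describe the patient's airway management and are obtained by asking the practitioner after intubation. Nothing is recorded per tooth on the predictor side. A logistic model of these predictors on dental trauma is, on an ordinary reading, one row per patient. The 3% to 5% figure then applies.

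**3. Grade set before the exposure.** Assume two equally common grades, a grade odds ratio of 3 for trauma, overall trauma 38.6%, exposure in 10% and 30% by grade, and no true exposure effect. The trauma risks by grade are then 0.2595 and 0.5125.

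- Exposed: (0.10 × 0.2595 + 0.30 × 0.5125)/0.40 = 0.449
- Unexposed: (0.90 × 0.2595 + 0.70 × 0.5125)/1.60 = 0.370
- Crude odds ratio: (0.449/0.551)/(0.370/0.630) = 1.39

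This is the most extreme case on the grid. With a grade odds ratio of 1.5 and exposure in 15% versus 25%, the crude value is 1.06. Reversing the direction gives 0.94 down to 0.70. In logistic simulations with 6,000 runs, the 15% versus 25% scenarios gave crude rejection of 4% to 9%, against 3% to 5% adjusted. Rates of 16% and 21% appeared only with a grade odds ratio of 3, a threefold exposure difference and trauma of 20% or 38.6%.

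**4. Grade set after the exposure.** Suppose a difficult airway draws a consultant: 80% versus 40% of cases, consultant odds ratio 0.5, direct difficulty odds ratio 2, baseline trauma 20%.

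- Difficult: 0.8 × 0.200 + 0.2 × 0.333 = 0.227
- Not difficult: 0.4 × 0.111 + 0.6 × 0.200 = 0.164
- Total odds ratio: (0.227/0.773)/(0.164/0.836) = 1.49, against 2.0 after adjustment

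With 60% versus 40% and a consultant odds ratio of 0.67, the total is 1.84. Here adjustment for grade answers a different question and corrects nothing.

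**5. Room for covariates.** At 5%, 20% and 38.6% trauma, 300 patients give 15, 60 and 116 events. Over nine terms that is 1.7, 6.7 and 12.9 events per term. A tenth term for grade lowers it to 1.5, 6.0 and 11.6.

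**6. The two operator sentences.** The first has each patient as its subject and can be read as one person ventilating and then intubating that patient. The second describes the pool from which that person came. Read so, they agree.

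**The case for a change.** The best argument for acting is that the omissions are real, are not redactions, and would be cheap to repair. No section supplies the unit, the covariates or the target effect. The cold-light examination is tooth by tooth, so an analyst could build a tooth-level file, and the plan names no clustered method to use with it. Whether an odds ratio is crude or adjusted affects its interpretation, and the grade example shows the same covariate removing bias in one setting and changing the question in another.

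What stands is that the model is under-described and that a report should say what was fitted. A tooth-level result, if one were reported, would need a method that allows for clustering on patient.

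What does not stand is the step from thin description to a wrong result. The large error rates belong to an analysis the plan does not describe. The grade argument rests on allocation, recording and effects about which the documents are silent. It also picks a variable not named as recorded, while Mallampati score, thyromental distance, mouth opening and previous difficult intubation are recorded before intubation and are more obvious candidates for adjustment. Those measures could confound a crude odds ratio whatever the role of grade, so adding grade alone would not make the estimates causal.

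**Conclusion.** The concern does not call for a change. The gap is one of detail in a secondary, exploratory analysis, and an analyst with 300 patients and patient-level predictors would sensibly fill it with one row per patient. On that basis the test size is 3% to 5%. The range of 6% to 35% applies only if teeth are entered as independent rows, and it rests on an assumed ICC of 0.05 to 0.30 and up to 12 teeth per patient.

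Confounding by operator grade is possible but not shown. The range of 1.06 to 1.39 (0.94 to 0.70 reversed) assumes that grade varies, precedes the exposure, and is related to both exposure and trauma. Where grade follows the exposure, adjustment would move a total odds ratio of 1.49 to 1.84 to a direct one of 2.0, which is no clear gain. The operator sentences are most likely loose wording for one anesthetist per patient. The methods are written in the past tense, so grade may not be retrievable in any case. The before-and-after comparison that serves the main aim is not biased by leaving grade out.
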